3.1.2 Other endpoints

- (1) Changes in mean Hb values from the first day of the treatment period at Weeks 48 and 52 of the treatment period
- (2) Proportion of subjects with a ≥ 1.0 g/dL increase in mean Hb values from the first day of the treatment period at each time point of the treatment period.
- (3) Number of days to maintain the target Hb values
- (4) Proportion of subjects receiving rescue therapy with ESA formulations, red blood cell transfusion, or phlebotomy
- (5) Study drug dosage

- (6) Total number of dosage adjustments
- (7) Iron supplement dosage
- (8) Proportion of subjects receiving oral, intravenous, or (any route) administration of iron supplements
- (9) Proportion of subjects with serum ferritin ≥ 100 ng/mL or TSAT $\geq 20\%$.
- (10) Changes and rate of changes in iron-related indices (serum iron, TIBC, TSAT, and serum ferritin values) and hepcidin from the first day of the treatment period
- (11) Changes in hematocrit, red blood cell count, reticulocytes (number and rate), mean corpuscular volume, mean corpuscular hemoglobin, and erythropoietin (MT-6548 group only) from the first day of the treatment period
- (12) Changes and rate of changes in systolic blood pressure, diastolic blood pressure, lipids (total cholesterol, LDL-C, HDL-C, LDL-C/HDL-C ratio, triglycerides), and blood glucose from the start of the treatment period
- (13) Change in renal function-related indices (eGFR, serum creatinine, urinary albumin/creatinine ratio) from the first day of the treatment period
- (14) QOL indices (EQ-5D-5L, KDQOL)

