8.1.2 Descriptive statistics to calculate

Types of continuous variables to be calculated for each descriptive statistics item are provided below. Number of subjects, mean, standard deviation (SD), median, minimum, maximum, and 2-sided 95% CI of the mean

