the treatment period.)" should be conducted for subjects continuously using iron supplements or iron-containing phosphate binders and subjects never using iron supplements and iron-containing phosphate binders during the treatment period. Analysis should be performed only in the MT-6548 group, and no analysis using the MMRM model will be conducted for patient cohorts. However, subjects who uses intravenous iron at least once should be excluded from the tabulation.

Since intravenous iron should be included in the tabulation for treatment period phase 1, the tabulation for treatment period phase 1 should be output again.

7) Analysis by iron supplements and iron-containing phosphate binders formulations

An analysis similar to "1) Treatment period Hb at each evaluation time point in the treatment period" except for the analysis using the MMRM should be conducted for subjects continuously using iron supplements or iron-containing phosphate binders during the treatment period. Analysis should be performed only in the MT-6548 group, and no analysis will be performed for patient cohorts. However, subjects who uses intravenous iron at least once should be excluded from the tabulation.

8) Analysis of Hb value at Week 52 and CRP values on the first day of the treatment period

For MT-6548 group only, a scatter plot chart should be provided after linear regression with the following variables. No analysis will be performed for patient cohorts.

x: Logarithmic CRP value on the first day of the treatment period

y: Hb values at Week 52 of the treatment period

(3) Proportion of subjects whose Hb level during the treatment period is within the target range (11.0 g/dL to <13.0 g/dL) or outside the target range (<10.0 g/dL or ≥ 13.0 g/dL)

The number, proportion, and 95% CI (Clopper-Pearson [Exact] method) of subjects with Hb value within the target range (11.0 g/dL to <13.0 g/dL, within), <11.0 g/dL (below), and ≥ 13.0 g/dL (above) at each time point of the treatment period should be provided by treatment group. McNemar tests should be used for before and after comparison (ratio of subjects within the target range and out of target range) on the first day and each evaluation time point of the treatment period.

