An analysis similar to “1) Study drug dosage” should be conducted for subjects using iron supplements or iron-containing phosphate binders continuously during the treatment period. Analysis should be performed only in the MT-6548 group, and no analysis will be performed for patient cohorts. However, subjects who use intravenous iron at least once should be excluded from the tabulation.

9) Analysis of the mean dose of the study drug at Week 48 to Week 52 of the treatment period and CRP values on the first day of the treatment period

For MT-6548 group only, a scatter plot chart should be provided after linear regression with the following variables. No analysis will be performed for patient cohorts.

x: Logarithmic CRP value on the first day of the treatment period

y: Study drug average dosage at Week 48 to Week 52 of the treatment period

(6) Total number of dosage adjustments

The number and proportion of subjects and the 95% CI (Clopper-Pearson [Exact] method) for the proportion of subjects receiving dose adjustment should be provided, after the first day of the treatment period, in each period between scheduled study visits and during the entire treatment period from the first day to Week 52 of the treatment period.

The number and proportion of subjects and the 95% CI (Clopper-Pearson [Exact] method) for the proportion of subjects should be provided for the proportion of subjects defined below in each period between scheduled study visits. If a subject is included in more than one definition, the subject should be counted in each definition.

No dose adjustment: No change

With dose adjustment: dose adjustment (Dose adjustment), dose increase (Increase), dose decrease (Decrease), drug interruption (Interrupt)

Dose adjustment (Dose adjustment) should include the number of times of increase, decrease, and interruption, and should not count the increase when it is resumed after interruption. Only the MT-6548 group will be tabulated.

(7) Iron supplement dosage

The following should be provided according to the 3 categories of oral iron supplement, intravenous iron supplement, and iron supplement (any route).

Descriptive statistics of the mean dose of iron supplement per month for each treatment group should be calculated for the screening period, and after the first day of the treatment period, in each period between scheduled study visits and during the entire treatment period from the first day to Week 52 of the treatment period.

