The number and proportion of subjects and 95% CI (Clopper-Pearson [exact] method) of the proportion of subjects with serum ferritin values of ≥ 100 ng/mL or TSAT of $\geq 20\%$ should be provided at each evaluation time point of the treatment period for each treatment group. Before and after comparison should be conducted for changes between the first day of the treatment period and each period between scheduled study visits using the McNemar test. Changes in iron-related measures (serum iron, TIBC, TSAT, and serum ferritin) and hepcidin should be calculated from the first day of the treatment period to each evaluation time point of the treatment period.

(10) Changes and rate of changes in iron-related indices (serum iron, TIBC, TSAT, and serum ferritin values) and hepcidin from the first day of the treatment period

Changes in iron-related measures (serum iron, TIBC, TSAT, and serum ferritin) and hepcidin should be calculated from the first day of the treatment period to each evaluation time point of the treatment period. A paired t-test should be performed for before and after comparison of changes and change rates from the first day of the treatment period.

A group comparison should be conducted for the change in iron-related measures (serum iron, TIBC, TSAT, and serum ferritin) and hepcidin from the first day of the treatment period to each evaluation time point using the MMRM (with compound symmetry [CS] for a covariance matrix within subject variance). LSMean, its standard errors, and 2-sided 95% CI should be calculated, and the point estimate, its standard errors, 2-sided 95% CI, and p-value should be provided for the group difference (MT- 6548 – darbepoetin) of the LSMean by treatment group. Only the serum ferritin value at each evaluation time point of the treatment period should be similarly compared between groups.

The time course diagram of changes in the iron-related measures (serum iron, TIBC, TSAT, and serum ferritin values) and hepcidin from the first day of the treatment period to each evaluation time point should be prepared for each treatment group. The 95% CI of LSMean will be represented by an error bar. For only the serum ferritin value, a time course diagram should be prepared for mean ferritin values and 95% CI at each evaluation time point of the treatment period.

The serum ferritin values should be shown as follows.

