(12) Changes in systolic blood pressure, diastolic blood pressure, and blood glucose from the start of the treatment period, changes and the rate of change in lipid (total cholesterol, LDL-C, HDL-C, LDL-C/HDL-C ratio, triglycerides) from the start of the treatment period

Systolic blood pressure, diastolic blood pressure, lipids (total cholesterol, LDL-C, HDL-C, LDL-C/HDL-C ratio, triglycerides), and blood glucose should be analyzed in the same manner as hematocrit, red blood cell count, and reticulocyte (number and rate) in the preceding section.

Descriptive statistics for each measurement at the evaluation time point of Week 52 of the treatment period should be calculated by baseline value (divided the number of subject into 3 categories at tertiles). And, the change from the first day of the treatment period should be obtained, and the descriptive statistics should be calculated for each dose group. A paired t-test should be performed for before and after comparison of changes from the first day of the treatment period. A group comparison should be conducted for the change from the first day of the treatment period using the MMRM (with compound symmetry [CS] for a covariance matrix within subject variance). LSMean, its standard errors, and 2-sided 95% CI should be calculated, and the point estimate, its standard errors, 2-sided 95% CI, and p-value should be provided for the group difference (MT-6548 – darbepoetin) of the LSMean by treatment group.

The descriptive statistics should be similarly calculated for each administration group on the rate of change from the first day of the treatment period at each evaluation time point of the lipid (total cholesterol, LDL-C, HDL-C, LDL-C/HDL-C ratio, triglycerides), and a group comparison should be

conducted using the MMRM (with compound symmetry [CS] for a covariance matrix within subject variance).

No analysis will be performed for patient cohorts.

(13) Renal function-related measures (eGFR, serum creatinine, urinary albumin/creatinine ratio) should be analyzed in the same way as hematocrit, red blood cell count, and reticulocyte (count and rate) in the previous section.

Renal function-related measures (eGFR, serum creatinine, urinary albumin/creatinine ratio) should be analyzed in the same way as hematocrit, red blood cell count, and reticulocyte (count and rate) in the previous section.

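### The within-arm t-test of percent change in iron markers and hepcidin does not test for no change: it leans towards a rise and does not hold its 5% level

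*SAP*

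**What the plan says.** **Iron markers and hepcidin.** Final SAP 3.1.2 (10) lists "Changes and rate of changes in iron-related indices" and hepcidin as an endpoint. Phase 1 SAP 3.1.3 (10) does the same. The protocol (5.4.1) lists only change from baseline, so the rate of change enters with the SAPs. For the test, Final SAP 8.5.2 (10) says: "A paired t-test should be performed for before and after comparison of changes and change rates". Phase 1 SAP 8.5.3 (10) has the same sentence.

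The comparison between arms is on another scale: "A group comparison should be conducted for the change in iron-related measures (serum iron, TIBC, TSAT, and serum ferritin) and hepcidin", by MMRM on the absolute change. The time-course figures also show absolute change (and, for ferritin, the measured values).

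**Lipids.** Final SAP 8.5.2 (12) and Phase 1 SAP 8.5.3 (12) ask for descriptive statistics and a between-arm MMRM "on the rate of change from the first day of the treatment period at each evaluation time point of the lipid". They state no within-arm t-test on the lipid rate.

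**Summaries and scale.** The standard descriptive set (8.1.2 in both SAPs) is "Number of subjects, mean, standard deviation (SD), median, minimum, maximum, and 2-sided 95% CI of the mean", with no geometric mean. No log transform or rank test is given for these markers. Logs appear only for CRP as a regressor ("Logarithmic CRP value on the first day of the treatment period"). Neither SAP defines the rate of change by formula. Section 8.1.3 displays it to one decimal, as it does percentages, so percent change from Day 1 is the natural reading.

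**The concern.** A paired t-test on percent changes asks whether their arithmetic mean is zero. That is a different question from whether the marker has changed. Percent change is lopsided: a doubling counts +100% and a halving only −50%, so one of each averages +25% although the two cancel as ratios. Any within-subject fluctuation therefore lifts the mean above zero, and a larger sample makes a significant result more likely without removing the bias.

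What is at stake is the within-arm p-value and mean for a named endpoint. The test can declare a rise when nothing has happened, and in a very variable marker it can miss a real fall. The same section also tests absolute change, so a reader could see the two scales disagree with no rule for reconciling them.

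**Working it through.** **Inputs.** Two-sided 5% level (8.1.1 in both SAPs). 150 subjects in one arm, the enrolment target in section 2.5 of both SAPs; fewer will have Week 24 or Week 52 values. The SD s of log(follow-up/Day 1) is an assumption, taken over 0.1 to 0.8, because the documents give no variability for these markers. They also state no power or error rate for percent change, so there is no figure of the plan's own to reproduce on this point.

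**Formula.** If log(follow-up/Day 1) is normal with mean d and SD s, then

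mean percent change = 100 × [exp(d + s²/2) − 1].

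- No true change (d = 0): 100 × [exp(s²/2) − 1], positive for every s > 0. At s = 0.5: exp(0.125) − 1 = +13.3%. At s = 0.8: exp(0.32) − 1 = +37.7%.
- True 20% geometric fall (d = log 0.8): 100 × [0.8 × exp(s²/2) − 1]. At s = 0.5: 0.8 × 1.133 − 1 = −9.3%. At s = 0.8: 0.8 × 1.377 − 1 = +10.2%.
- Geometric fall that averages to exactly zero: 1 − exp(−s²/2), which is 2.0% at s = 0.2, 16.5% at 0.6 and 27.4% at 0.8.

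**Rejection rates.** One-sample t-tests on simulated data, n = 150, 40,000 runs per cell. Runs of 4,000 to 8,000 differ by a point or so.

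| s | Mean % change, no true change | Significant rise, no true change | Mean % change, true 20% fall | Fall detected, percent scale | Fall detected, log ratio |
|---|---|---|---|---|---|
| 0.1 | +0.5% | 8% | −19.6% | 100% | 100% |
| 0.2 | +2.0% | 21% | −18.4% | 100% | 100% |
| 0.3 | +4.6% | 40% | −16.3% | 100% | 100% |
| 0.5 | +13.3% | 80% | −9.3% | 65% | >99% |
| 0.8 | +37.7% | 99% | +10.2% | 0.3% | 93% |

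A valid two-sided 5% test gives a false rise in 2.5% of trials. The t-test on the log ratio gives about 2.5% at every s. At s = 0.8 with a true 20% fall, the percent-scale test declares a significant rise in about 17% of trials.

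**Does this need the log-normal model?** The direction does not. If Day 1 and follow-up values X0 and X1 are positive and exchangeable, E[X1/X0] = E[X0/X1]. Since r + 1/r is at least 2, each expectation is at least 1. With independent values uniform on 50 to 150, which are not skewed at all, the mean percent change is about +10% and the median about 0.

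**Lipid comparison between arms.** With no true change in either arm, the difference in mean percent change is 100 × [exp(s₁²/2) − exp(s₀²/2)]. It is zero when the SDs are equal. With 0.6 against 0.4 it is 119.7 − 108.3 = +11.4 points.

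**The case against.** Several objections stand and limit the point.

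- **Reach.** A reader might infer that the iron-marker comparison between arms is biased. It is not biased by this mechanism: that MMRM uses absolute change, as do the change-from-Day-1 figures. The change rate gets one within-arm test, beside the same test on absolute change.
- **Weight.** These are other endpoints, and Phase 1 SAP 8.5.4.7 calls the analyses of secondary and other endpoints exploratory. The primary Hb analysis does not depend on them. This lowers the weight, but it does not make a test stated at 5% hold 5%.
- **Size.** It rests wholly on an assumed s. At s of 0.1 to 0.2 the bias is only 0.5% to 2.0%, and a 20% fall is found essentially always up to s = 0.3. A reader might infer that real falls will generally vanish or reverse. Of the values tabulated, a 20% fall changes sign only at s = 0.8. With fewer than 150 subjects the false-rise rates would be lower, but the mean bias would be the same.
- **Cause.** Skewness of the marker is a tempting explanation. The driver is the within-subject variability of the ratio, as the uniform example shows.
- **Display.** The median is in the standard set and is not distorted in this way. But 8.5.2 (10) does not itself order descriptive statistics of the change rate, and the p-value attaches to the mean.
- **Absolute change.** If the ratio is independent of Day 1, the mean absolute change also drifts upward. With an assumed log-baseline SD of 0.8, false rises occur in about 22%, 52% and 87% of trials at s = 0.3, 0.5 and 0.8. So the absolute-change test is sound when a marker's distribution is the same at both visits, not under every model. The percent-change bias is present under both.
- **Clinical premise.** A reader might add that a fall in hepcidin or ferritin is the effect being sought. The documents do not say so, and the point does not need it.
- **Lipids.** With no true change, the arm comparison is distorted only if variability differs between arms. The documents give no evidence that it does.

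The CRP regressions lend little support either way: logging a regressor does not settle the scale of an outcome.

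**Conclusion.** The point holds for the within-arm paired t-test on the change rate of serum iron, TIBC, TSAT, ferritin and hepcidin, in both SAPs. Its null hypothesis is not that nothing changed, and its error runs towards a rise. Even at s = 0.1 the false-rise rate is about three times the nominal 2.5%, although the bias in the estimate is then trivial. By s = 0.5 the bias is material (+13.3%) and the test is unreliable.

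This rests on reading the change rate as percent change from Day 1, on n = 150, and on a log-normal ratio for the exact figures; the direction also holds for any positive exchangeable pair. Which markers are variable enough to matter cannot be settled from the documents.

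For lipids, the descriptive mean percent change carries the same upward bias. The arm comparison is at risk only under the condition given above. No conclusion on Hb is affected. The change should be made because it is cheap and the planned test is wrong as written, but it concerns exploratory results.

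**What to change.** In Final SAP 8.5.2 (10) and (12), and Phase 1 SAP 8.5.3 (10) and (12):

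1. Define the rate of change by formula.
2. For the iron markers and hepcidin, run the paired t-test on log(follow-up/Day 1). Back-transform and report geometric mean percent change with its 95% CI.
3. For lipids, run the rate-of-change MMRM on log(follow-up/Day 1) with the log Day 1 value as covariate. Report geometric mean percent change by arm and the between-arm geometric mean ratio, each with a 95% CI.
4. Keep the absolute-change analyses as planned.

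The cost is SAP wording and one transformation in the code, with no new data. Logs remain available for low values, because section 7.5 of both SAPs replaces results below the quantification limit with a positive substitute. Protocol 13.4 requires the reason for such a change to be recorded and, after data lock, the results to be kept apart from the original plan. The one small downside is that the reported figure becomes a geometric rather than an arithmetic percent change, which the table footnotes should say.

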Hb value and change of Hb values from the first day of the treatment period at each evaluation time point of the treatment period will be obtained, and its descriptive statistics should be calculated for each treatment group. Before and after comparison will be conducted for changes of Hb from the first day of the treatment period to each evaluation time using the paired t-test. In the Conversion and Conversion ($Hb \geq 11.0$ g/dL) cohorts, no test will be conducted for the difference between the baseline value and each evaluation time point during the treatment period in the darbepoetin alfa group.

A group comparison should be conducted using an MMRM (with compound symmetry [CS] for a covariance matrix within subject variance) similar to the analysis of “(1) Mean Hb values at Week 48 and Week 52 of treatment”. LSMean, its standard errors, and 2-sided 95% CI will be calculated for Hb value at each evaluation time point of the treatment period, and the point estimate, its standard errors, 2-sided 95% CI, and p-value will be calculated for the group difference (MT-6548 – darbepoetin) of the LSMean by treatment group.

A group comparison should be conducted for the change from the first day of the treatment period using the MMRM (with compound symmetry [CS] for a covariance matrix within subject variance). LSMean, its standard errors, and 2-sided 95% CI should be calculated for change at each evaluation

time point from the first day of the treatment period, and point estimate, its standard errors, 2-sided 95% CI, and p-value should be calculated for the group difference (MT-6548 – darbepoetin).

The time course diagram will be prepared for mean Hb values in each evaluation time point in the treatment period by treatment group. 95% CI of the mean will be represented by an error bar.

In the Conversion and Conversion ($Hb \geq 11.0$ g/dL) cohorts, no test will be conducted for the group difference.

2) Analysis of timing of administration of MT-6548 tablets (before meal, after meal, other)

An analysis similar to “1) Treatment period Hb at each evaluation time point in the treatment period” should be conducted by the timing of administration of MT-6548 tablets (before meal, after meal, other). However, this analysis is only for the MT-6548 group; neither tabulation in the darbepoetin group nor comparison with the darbepoetin group is performed. No analysis will be performed for patient cohorts.

3) Analysis by previous ESA formulation type

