An analysis similar to “1) Treatment period Hb at each evaluation time point in the treatment period” should be conducted by the type of previous ESA formulation (epoetin alfa or epoetin beta, darbepoetin alfa, epoetin beta pegol). Only Conversion, Conversion ($Hb \geq 11.0$ g/dL), and Conversion ($Hb < 11.0$ g/dL) cohorts should be analyzed, and the data should be summarized in the MT-6548 group only.

4) Analysis by dose of previous ESA formulation types

An analysis similar to “1) Treatment period Hb at each evaluation time point in the treatment period” should be conducted for weekly dose of previous ESA formulation (darbepoetin alfa, epoetin beta pegol: ≥ 15 µg, < 15 µg; 2 categories) by type of previous ESA formulation (darbepoetin alfa, epoetin beta pegol). The number of patients classified by dose was set to be almost equal.

Only Conversion, Conversion ($Hb \geq 11.0$ g/dL), and Conversion ($Hb < 11.0$ g/dL) cohorts should be analyzed, and the data should be summarized in the MT-6548 group only.

5) Analysis of Hb value on the first day of the treatment period

An analysis similar to “1) Treatment period Hb at each evaluation time point in the treatment period” should be conducted for the Hb value on the first day of the treatment period (divided the number of subject into 3 categories at tertiles). The Conversion ($Hb < 11.0$ g/dL) cohort should be summarized in the MT-6548 group only. Time course diagram for mean and 95% CI should be prepared separately by treatment group. No statistical test will be conducted for the group difference and the difference between baseline and each evaluation time point in the treatment period for the darbepoetin alfa group in the Conversion cohort and Conversion ($Hb \geq 11.0$ g/dL) cohort.

6) Analysis with or without iron supplements and iron-containing phosphate binders

An analysis similar to “1) Treatment period Hb at each evaluation time point in the treatment period (LSMean, standard error, and two-sided 95% CIs will not be calculated for changes from the start of

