An analysis similar to the above should be conducted for serum ferritin at baseline (divided the number of subject into 3 categories at tertiles). Time course diagram for mean and 95% CI should be prepared separately by treatment group.

The following scatter plot chart should be provided by treatment group. Linear regression should be performed to calculate the p-value and correlation coefficient of the test with zero slope as the null hypothesis.

x: Serum ferritin at baseline

y: Serum ferritin at Week 52 of the treatment period

(11) Change in hematocrit, red blood cell count, reticulocyte (count and rate), mean corpuscular volume, mean cell hemoglobin, and EPO (MT-6548 group only) from the first day of the treatment period

Descriptive statistics of hematocrit, red blood cell count, reticulocyte (count and rate), mean corpuscular volume, mean cell hemoglobin, and EPO (MT-6548 group only) at each evaluation time point should be calculated for each dose group. And, the change from the first day of the treatment period should be obtained, and the descriptive statistics should be calculated for each dose group. A

paired t-test should be performed for before and after comparison of changes from the first day of the treatment period.

A group comparison should be conducted for the change in hematocrit, red blood cell count, reticulocyte (number and rate), mean corpuscular volume, mean corpuscular hemoglobin, and EPO (MT-6548 group only) from the first day of the treatment period to each evaluation time point using the MMRM (with compound symmetry [CS] for a covariance matrix within subject variance). LSMean, its standard errors, and 2-sided 95% CI should be calculated, and the point estimate, its standard errors, 2-sided 95% CI, and p-value should be provided for the group difference (MT-6548 – darbepoetin) of the LSMean by treatment group. EPO will be analyzed in the MT-6548 group only. Hematocrit, RBC count, and reticulocytes (number and rate) in the Conversion (Hb < 11.0 g/dL) cohort should be analyzed only in the MT-6548 group. No statistical test should be conducted for hematocrit, RBC count, and reticulocytes (number and rate) in the Conversion cohort and Conversion (Hb \geq 11.0 g/dL) cohort for group differences and the difference between baseline and each evaluation time point in the treatment period for the darbepoetin alfa group.

A histogram of EPO measurements should be prepared for evaluation time point at Week 52 of the treatment period.

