8.5.4 Statistical analysis issues

8.5.4.1 Adjustment for covariates

In the analysis of efficacy, in order to consider the effect of the measurement value of the first day of the treatment period on the change of each measurement in the group comparison, the analysis using the MMRM should be conducted using the measurement value of the first day of the treatment period as a covariate in the general analysis.

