(12) Changes in systolic blood pressure, diastolic blood pressure, and blood glucose from the start of the treatment period, changes and the rate of change in lipid (total cholesterol, LDL-C, HDL-C, LDL-C/HDL-C ratio, triglycerides) from the start of the treatment period

Systolic blood pressure, diastolic blood pressure, lipids (total cholesterol, LDL-C, HDL-C, LDL-C/HDL-C ratio, triglycerides), and blood glucose should be analyzed in the same manner as hematocrit, red blood cell count, and reticulocyte (count and rate) in the preceding section.

Descriptive statistics for each measurement at the evaluation time point of Week 24 of the treatment period should be calculated by baseline value (divided the number of subjects into 3 categories at tertiles). In addition, the change from the first day of the treatment period should be obtained, and the descriptive statistics should be calculated for each dose group. A paired t-test should be performed for before and after comparison of changes from the first day of the treatment period. A group comparison should be conducted for the change from the first day of the treatment period using the MMRM model (with compound symmetry [CS] for a covariance matrix within subject variance). The LSMean of by treatment group should be calculated, and the point estimate of between-group differences (MT-6548 – darbepoetin), its standard errors, 2-sided 95% CI, and p-value of LSMean should be provided.

The descriptive statistics should be similarly calculated for each administration group on the rate of change from the first day of the treatment period at each evaluation time point of the lipid (total cholesterol, LDL-C, HDL-C, LDL-C/HDL-C ratio, triglycerides), and a group comparison should be conducted using the MMRM model (with compound symmetry [CS] for a covariance matrix within subject variance).

No analysis will be performed for patient cohorts.

(13) Change in renal function-related measures (eGFR, serum creatinine, urinary albumin/creatinine ratio) from the first day of the treatment period

Renal function-related measures (eGFR, serum creatinine, urinary albumin/creatinine ratio) should be analyzed in the same way as hematocrit, red blood cell count, and reticulocyte (count and rate) in the previous section.

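### Within-arm paired t-tests of change from Day 1, run inside tertiles of the same Day 1 value, will show regression to the mean as significant change in the outer tertiles

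*SAP*

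**What the plan says.** **Hb.** Final SAP 8.5.1 (2) 1) asks for a before/after comparison "for changes of Hb from the first day of the treatment period to each evaluation time using the paired t-test", alongside a between-arm MMRM. Item 5) of the same section repeats that analysis by tertile: it "should be conducted for the Hb value on the first day of the treatment period (divided the number of subject into 3 categories at tertiles"). Item 5) then withdraws two tests in the Conversion and Conversion (Hb ≥11.0) cohorts: the test of the group difference and the darbepoetin before/after test. In Conversion (Hb <11.0) only the MT-6548 group is summarised.

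**Serum ferritin.** Final SAP 8.5.2 (10) specifies a paired t-test and an MMRM, then says: "An analysis similar to the above should be conducted for serum ferritin at baseline (divided the number of subject into 3 categories at tertiles"). Baseline is not separately defined here. The efficacy subgroup table (Table 8.5.4.5.1) cuts ferritin at tertiles of the Day 1 value, so Day 1 is the natural meaning.

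**Blood pressure, lipids, glucose.** Final SAP 8.5.2 (12) says that Week 52 descriptive statistics "should be calculated by baseline value (divided the number of subject into 3 categories at tertiles"). The next sentences say that "the change from the first day of the treatment period should be obtained", add a paired t-test, and continue: "A group comparison should be conducted for the change from the first day of the treatment period using the MMRM".

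**Phase 1 SAP.** Sections 8.5.2 (1) 1) and 5) and 8.5.3 (10) and (12) carry the same plan to Week 24, including the sentence "A paired t-test should be performed for before and after comparison of changes from the first day of the treatment period".

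**Covariate.** Final SAP 8.5.4.1 says that "the analysis using the MMRM should be conducted using the measurement value of the first day of the treatment period as a covariate". Neither SAP mentions regression to the mean or cautions against reading the within-tertile paired tests as treatment effects.

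**The concern.** The variable that defines the groups is also the value subtracted to form the change. A reading in the top third of a sample is there partly by chance (biological variation, assay error, time of day). A second reading on the same people is lower on average even if nothing has happened, and the bottom third rises in the same way. A one-sample test of change against zero cannot separate this from a drug effect.

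At stake is how the exploratory tables are read. Blood pressure or LDL-C falling in subjects who began high, or Hb falling from the top third and rising from the bottom third, would carry small p-values and look like an effect that depends on baseline level. For Hb in patients switched from an ESA, convergence from both ends is also what successful maintenance would look like, and switch maintenance is a stated objective.

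**Working it through.** **The plan's own figure.** The SAPs give no figure for the tertile analyses. The only stated figure is the joint probability above 95% for the primary endpoint (sample-size rationale, section 2.5 of each SAP). It reproduces: 0.75 / (1.78 × √(2/150)) = 0.75 / 0.2055 = 3.65; 3.65 − 1.96 = 1.69; power = 95.4%. The chance that the MT-6548 CI lies in 11.0–13.0 g/dL is above 99.999%, and the joint probability by simulation is 95.5%. None of this depends on the tertile tests.

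**Inputs.** Two-sided 5% level (8.1.1). 150 per arm, so about 50 per tertile. Conversion cohort target 200, so about 100 per arm and 33 per tertile. Conversion (Hb ≥11.0) cap 120, so about 60 per arm and 20 per tertile (section 2.5). The correlation r is assumed, range 0.9 to 0.5. Day 1 and later values are taken as bivariate normal with equal means and SDs, so there is no true change.

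**Shift.** The mean of the top third of a standard normal is φ(0.431)/(1/3) = 1.091. The expected change there is −1.091 × (1 − r) SD, with the opposite sign in the bottom third.

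**Spread of the change within the tertile.** √[(1 − r²) + (1 − r)² × v], where v = 1 + 0.431 × 1.091 − 1.091² = 0.280 is the variance of the Day 1 value within the third.

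**Example, r = 0.8, n = 50.** Shift 1.091 × 0.2 = 0.218 SD. Spread √(0.36 + 0.04 × 0.280) = 0.609 SD. Non-centrality 0.218 / 0.609 × √50 = 2.53. Rejection probability 69.9%.

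| r | Shift (SD) | n = 50 (all subjects) | n = 33 (Conversion) | n = 20 (Conversion, Hb ≥11.0) |
|---|---|---|---|---|
| 0.9 | 0.11 | 41% | 28% | 18% |
| 0.8 | 0.22 | 70% | 51% | 33% |
| 0.7 | 0.33 | 87% | 70% | 48% |
| 0.5 | 0.55 | 99% | 92% | 72% |

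Simulation agrees to within about two percentage points: about 40–98%, 27–92% and 19–71% across the three columns. At r = 0.95 and n = 50 the rate is still 22.6%. With dropout to 40 per tertile it is 33.5% to 96.0% over r = 0.9 to 0.5.

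**Where the level holds.** In the same simulations (150 per arm), the middle tertile rejects in 5–6% and the unsplit paired test in 4.5–5.6%. The between-arm contrast within an outer tertile, adjusted for Day 1, rejects in 4.9–6.0%; a single-visit ANCOVA stood in for the MMRM.

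**Number of tests.** In 8.5.2 (12) alone: 8 measures × 2 outer tertiles × 2 arms = 32 tests at Week 52, with no multiplicity control.

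**Screening tertiles as an alternative.** The residual shift is 1.09 × [r(screening, Day 1) − r(screening, Week 52)] SD. Assumed examples, 150 per arm, with Week 52 equally correlated with screening and with Day 1:

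- equal correlations throughout: about 5%
- 0.80 to Day 1, 0.70 to Week 52: 16–17%
- 0.85 and 0.70: 31–33%
- 0.80 and 0.60: 40–41%

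**The case against.** **The text of 8.5.2 (12) does not say that the t-test is run within tertiles.** This is true: its tests are described by dose group. However, the first paragraph of (12) already sends the unsplit analysis, with its own paired t-test and MMRM, to the method of item (11). The second set would be redundant unless it belongs to the tertiles. That is the most natural reading but not a certain one. For Hb and ferritin there is no such doubt.

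**The randomised comparison is sound.** This stands. The artefact arises equally in both arms and cancels in the Day 1-adjusted difference. A reader might infer that the MT-6548 minus darbepoetin estimates or the non-inferiority result are biased; the documents give no support for that.

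**The analyses are exploratory.** The Phase 1 SAP says so in 8.5.4.7. The long-term safety summaries of laboratory values and vital signs (Final SAP 8.6.2, 8.6.6) use neither tertiles nor paired tests. It would go too far to say that the safety objective is compromised.

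**Hb and ferritin are actively managed.** Hb is titrated to a target range in both arms and iron is given to a ferritin or TSAT threshold, so some movement in the outer tertiles is intended. A reader might infer that all such movement would be artefact; that does not follow. What follows is that the paired test cannot tell the two apart.

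**Darbepoetin is still displayed.** In the Conversion and Conversion (Hb ≥11.0) cohorts, time courses by tertile are drawn for each arm, so a shared pattern could be seen. A reader might infer that all comparator information is dropped there. The SAP drops the tests, and does not clearly say whether the estimated difference and its CI are dropped too. The only p-value left is still the uninterpretable one.

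**Conclusion.** The point holds for one procedure: the within-arm paired t-test of change from Day 1 inside the outer tertiles of Day 1. It is explicit for Hb and serum ferritin in both SAPs and the most natural reading for blood pressure, lipids and glucose.

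Inflation is present at every correlation examined. Its size rests on the assumed r, on normality and on equal spread at the two visits. Eligibility limits on Hb make the Conversion-cohort figures approximate.

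The practical weight is greatest for Hb tertiles in the Conversion and Conversion (Hb ≥11.0) cohorts, where this is the only test retained. Elsewhere a valid between-arm analysis sits beside it. The consequence is misleading exploratory p-values.

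**What to change.** In both SAPs, delete the paired t-test from every analysis by tertile of the baseline value: Hb, serum ferritin, blood pressure, lipids and glucose. Keep within-tertile change as descriptive statistics, with both arms side by side. Report the Day 1-adjusted between-arm difference with its 95% CI within tertiles, including the Hb tertiles in the Conversion and Conversion (Hb ≥11.0) cohorts. State in 8.5.2 (12) of the Final SAP and 8.5.3 (12) of the Phase 1 SAP which analyses are by tertile.

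Forming the tertiles on a screening value should not be relied on instead. It reduces the artefact but restores the 5% level only if correlation does not decay between Day 1 and Week 52. Also, protocol 9.2.4.1 lists vital signs for the CRF only from Day 1, so a screening blood pressure may not be in the data.

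The cost is the loss of some exploratory within-arm p-values and an entry explaining the change, as protocol 13.4 requires. No new data are needed and the primary analysis is untouched.
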